## **B. Scheduled Visits**

When a subject is first identified during a visit or when reviewing a 24-48 hour or 2-week ambulatory ECG monitor (Zio Patch), we request that sites briefly screen the subject by reviewing the inclusion/exclusion criteria of the protocol. Assessment of calculated LVEF (obtained by transthoracic echocardiogram) and PVC burden is acceptable as long as it has been obtained within the prior 150 days. If the subject meets both, then the subject should be scheduled for a Baseline Visit (Observation – Visit 1).

Subjects enrolled in the study will have visits as outlined in Table 2 and Figure 1. There are some circumstances where the screening and Observation Visit 1 may occur the same day.

*i. Observation – Visit 1.* After inclusion/exclusion criteria is confirmed, the study protocol will be explained to the subject and informed consent should be obtained. If the subject agrees to participate, the following data should be collected using appropriate forms (see Data collection forms), including general info and demographics, current medical therapy, physical exam, NYHA functional class and Minnesota HF quality of life questionnaire (QOL). Physical examination and NYHA functional class can be completed

based on a prior visit (up to 120 days prior). A 12-lead electrocardiogram and cardiac MR should be requested if clinically indicated. Alternatively, we will request that sites provide images of prior ECG or CMR if performed within the prior 120 days. Sites should obtain a copy of the transthoracic echo (during screening Visit) and mail it to the Echo Core laboratory led by [name] III, M.D. The Echo report should be uploaded to REDCap. Finally, a 2-week Zio Patch (IRhythm ambulatory ECG device) should be placed on the subject to obtain a long-term PVC burden. The subject will mail the device to IRhythm for analysis. Instructions will be provided to all centers on the placement of this device.

During this 3-month observation period, all subjects are allowed to titrate medical therapy to be optimized or continue on *optimal medical therapy* throughout the study. We define *optimal medical therapy* as maximal tolerated/recommended target doses of beta blockers (carvedilol 25mg twice daily, metoprolol succinate / tartrate 200mg daily or bisoprolol 10mg daily), angiotensin converting enzyme (ACE) inhibitors (lisinopril 20-40mg daily, ramipril 10mg daily, enalapril 10-20mg twice daily or quinapril 40mg twice daily) or angiotensin receptor blockade (ARB, valsartan 160mg twice daily or candesartan 32mg daily), aldosterone antagonists (spironolactone 25mg daily or eplerenone 25mg daily) and loop diuretics if indicated to achieve dry weight. Entresto (sacubitril 49-97mg/valsartan 51-103mg bid) could be used if clinically indicated. Except for non-dihydropyridine calcium-channel blockers (CCB, amlodipine and felodipine), diltiazem, verapamil, and nifedipine (dihydropyridine CCB) are not allowed during the study due to negative inotropic effect. Class Ia AADs will not be allowed during study due to risk of proarrhythmia.

During this visit, randomization to either antiarrhythmic drugs (AADs) or radiofrequency ablation (RFA) will be obtained. If the subject is assigned to the RFA arm, we request that the RFA procedure be scheduled at 3-months from this visit (Treatment – Visit 1). All subjects should be optimized or continue current medical therapy without change. If the subject is randomized to antiarrhythmic therapy (see Section C: Description of the intervention/treatment), this should be withheld until the 3-month observation period is completed.

ii. *Observation – Visit 2.* During this visit, subjects are asked to return to have a repeat Zio Patch (2-week ECG monitor) and ECG (if clinically indicated). Similarly, subjects will be instructed to mail back the Zio Patch to IRhythm, for assessment of PVC burden. At this time, a transthoracic echocardiogram should be scheduled in preparation for Observation – Visit 3.

iii. *Observation – Visit 3.* Similar to Visit 1, appropriate data collection forms should be used to collect current medical therapy, NYHA functional class and Minnesota HF quality of life questionnaire (QOL). 12-lead ECG should be obtained if clinically indicated. Transthoracic echocardiogram should be performed to assess LVEF and a copy mailed to the Echo Core laboratory led by [name] III, M.D. The local PI and designated site staff will be able to log in to iRhythm's ZioReports to obtain the Zio Patch report that should include a 2-week PVC burden.

[figure not shown]
If PVC burden remains  $\geq 10\%$  and LVEF  $\leq 45\%$ , then the subject will either initiate antiarrhythmic drugs or undergo RFA procedure (see Section C: Description of the intervention/treatment) and will continue on protocol as scheduled. However, if these criteria are no longer met, the subject is considered a screen failure and is withdrawn from the study. In such a case, the treatment decision is solely at the discretion of the electrophysiologist caring for subject. Nevertheless, this subject will be included in a PVC-CM registry if consent was provided (described above Section A.1).

i) *Treatment – Visit 1.* This is considered the baseline visit where PVC suppression strategy assignment is initiated (either RFA or AADs). If the subject is randomized to RFA, we will request that sites complete the RFA data collection form which includes information during the RFA procedure as well as recovery, complications and hospital stay. EPS will be performed on their baseline medications, except for antiarrhythmic drugs class II (beta blockers) which will be held at least 5 half-lives prior to procedure. Beta blockers should be resumed after RFA.

iv. However, subjects randomized to AADs can have this visit combined with Observation-Visit 3. In addition, subjects in the antiarrhythmic (AAD group) will require a baseline TSH and LFTs (AST only) if amiodarone is chosen.

v. *Treatment – Visit 2.* Using appropriate data collection forms, we will ask that sites obtain current medical therapy information, NYHA functional class and Minnesota HF quality of life questionnaire (QOL). 12-lead ECG should be obtained if clinically indicated. A repeat Zio Patch should be placed to re-assess adequate PVC suppression after RFA or initiation of AADs. The local PI and designated site staff will be able to log in to iRhythm’s ZioReports) 3 weeks later to obtain a Zio Patch Report with repeat PVC burden after intervention. If PVC burden is suppressed by more than 80%, intervention is considered successful and the subject should continue with treatment visits as scheduled,

However, if PVC burden does not decrease by more than 80%, intervention is considered a failure. In such a case, the subject should be considered for a second RFA procedure or a different antiarrhythmic drug depending on the randomization group that the subject was assigned (see Section C: Description of the Intervention/treatment). We discourage crossover of treatment arms since this will result in automatic withdrawal from the study. Nevertheless, subjects that withdraw from the study will be included in a PVC-CM registry if the subject provided consent. (described above Section A.1).

**Figure 1.** PAPS study design. A 3-month Observation (Obs) period allows each subject to serve as their own control to assess benefits of PVC suppression. All subjects will be randomized (R) to either RFA or AADs. OMT, optimal medical therapy. QOL, quality of life questionnaire; NYHA, New York Heart Association class; LVEF, LV ejection fraction; Zio, ambulatory ECG Ziopatch Holter, CMR, Cardiac MRI (\*, visit/intervention if clinically indicated).

vi. *Treatment – Visit 3.* Appropriate data collection forms should be used to collect current medical therapy information, NYHA functional class and Minnesota HF quality of life questionnaire (QOL). 12-lead ECG should be obtained if clinically indicated. A transthoracic echocardiogram should be performed to assess LVEF and a copy mailed to the Echo Core laboratory led by [name] III, M.D. A repeat Zio Patch should be placed to re-assess PVC burden. Local PI and designated site staff will be able to log in to iRhythm’s ZioReports 3 weeks later to obtain a Zio Patch Report if desired for any clinical decision.

vii. *Treatment – Visit 4.* Appropriate data collection forms should be used to collect current medical therapy information, NYHA functional class and Minnesota HF quality of life questionnaire (QOL). 12-lead

ECG should be obtained if clinically indicated. If clinically indicated, a transthoracic echocardiogram should be performed to assess LVEF and a copy mailed to the Echo Core laboratory led by [name] III, M.D. A repeat Zio Patch should be placed to re-assess PVC burden. The local PI and designated site staff will be able to log in to iRhythm's ZioReports 3 weeks later to obtain a Zio Patch Report if desired for any clinical decision. In addition, subjects in the antiarrhythmic (AAD group) will require a follow-up TSH and LFTs if amiodarone is part of the current treatment.

viii. *Treatment – Visit 5.* Using appropriate data collection forms, we will ask that sites obtain current medical therapy information, NYHA functional class and Minnesota HF quality of life questionnaire (QOL). 12-lead ECG should be obtained if clinically indicated. If a transthoracic echocardiogram is performed for any reason prior to this visit, we will ask that sites mail a copy to the Echo Core laboratory ([name] III, M.D.).

ix. *Treatment – Visit 6.* Using appropriate data collection forms, we will ask that sites obtain current medical therapy information, NYHA functional class and Minnesota HF quality of life questionnaire (QOL). 12-lead ECG should be obtained if clinically indicated. A final, transthoracic echocardiogram should be performed to obtain assessment of LVEF and images should be sent to the Echo Core laboratory ([name].). A repeat Zio Patch should be placed to re-assess PVC burden. The local PI will be able to log in to iRhythm's ZioReports to obtain a Zio Patch Report if thought to be needed for treatment decisions. In addition, subjects in the antiarrhythmic (AAD group) will require a follow-up TSH and LFTs if amiodarone is part of the current treatment.

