**Table 2. Table of Study Procedures**

	3-month Observation			12-month Treatment Phase					
	Obs-V1 Baseline	Obs-V2 2-mo	Obs-V3 3-mo	Tx-V1 Baseline	Tx-V2 1-mo	Tx-V3 3-mo	Tx-V4 6mo	Tx-V5 9-mo*	Tx-V6 12-mo
Timeline in Weeks (range of days)	Week 0 (Day 0)	Week 9 (51-63)	Week 12 (84-96)	Week 12-15 (84-105)	Week 21 (141-153)	Week 26 (176-188)	Week 38 (260-272)	Week 50 (344-356)	Week 64 (441-454)
Informed consent	X								
Inclusion/Exclusion Criteria	X								
Collection of demographic data	X								
Medical History	X								
Physical Exam	X		X		X	X	X	X	X
Functional status/NYHA class	X		X		X	X	X	X	X
QOL Minnesota HF Questionnaire	X		X		X	X	X	X	X
Current / change of medications	X		X		X	X	X	X	X
12-lead ECG	X*	X*	X		X*	X*	X*	X*	X*
Ziopatch	X	X ‡			X €	X	X		X
Echo	X £		X ‡			X	X*		X
BNP / ProBNP levels ESR & CRP	X* £		X*		X*	X*	X*	X*	X*
Urine pregnancy test (if applicable)	X		X	X	X	X	X	X	X
CMR	X*								
TSH (if assigned to amiodarone)			X				X		X
LFT (AST) (if assigned to amiodarone)			X				X		X
Treatment randomization	X								
Initiation of RFA or ADD				X					

Collection of unsolicited AEs	From Obs-Visit 1 until Tx-Visit 6
--------------------------------------	-----------------------------------

Footnote: \*, visit/intervention if clinically indicated.

‡ LVEF results of 2D-echocardiogram and Ziopatch have to be available at the time of Observation Visit 3 (Obs-V3). € If PVC burden >10%, subject should be considered to either adjust antiarrhythmic therapy (AAD group) or second ablation procedure (RFA group) based on their randomization group. ESR, Erythrocyte sedimentation rate; CRP, C-reactive protein. £ Must be done within 150 days of Enrollment Visit (Day 0)

Crossover between PVC suppression strategies is not encouraged. We request that crossover only be considered after 6 months of initiation of treatment, for which an intention-to-treat analysis will be performed. However, if crossover occurs before 6 months of initiation of treatment, subjects will be withdrawn from the study and included in the PVC-CM registry if the subject provided consent.

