c.4. Cardiovascular magnetic resonance (CMR). If clinically indicated, a delayed enhancement CMR will be performed at each center following a single protocol (approved by CMR core laboratory Director: [name], Richmond, VA) and sent to the CMR core lab for final interpretation. Similarly, CMR core lab and participants will remain blinded to group assignment. CMR will be obtained at baseline if clinically indicated to assess LV volumes, mass, ejection fraction, and mid-wall circumferential strain; overall myocardial T1, T2, and extracellular volume fraction (ECV); and scar location and extent using late gadolinium enhanced methods according to previously published techniques. Associations between each CMR assessment and improvement in LV function (responders) will be determined after PVC suppression strategy. Interstitial myocardial fibrosis and outcomes between early- vs. late-coupled PVCs in an attempt to support a mechanistic aim in final PAPS study. The CMR will be considered clinically indicated to exclude other types of cardiomyopathy, and all sites have agreed to order CMR on enrolled subjects.

c.5. Minnesota living with heart failure quality of life (QOL) and NYHA functional class questionnaires to be used in the PAPS study will be approved by [name] (Heart failure core lab). These questionnaires will be provided to each center to be answered by each subject in their local institution. This will allow us to assess heart failure symptoms and change in quality of life and functional status during the observation period and between both treatment groups. Questionnaires will be sent directly to the Heart failure core lab. *All QOL and NYHA questionnaires will be evaluated and graded by an event adjudication committee (independent of the steering committee, see Section G. Ethical / Regulatory Affairs). If clinically indicated, we will request to provide brain natriuretic peptide (BNP) levels as well as CRP and ESR as per schedule on Table 2.* Participants who are evaluated by study staff and suspected to be depressed will be referred to a primary care provider to facilitate the evaluation.

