#### **E. Primary and secondary outcome measures.**

*The outcomes are divided in primary and secondary end-points (Table 3).*

*The primary end-points will consist of:*

1. *Improvement of LVEF after PVC suppression at 12-month follow-up.* This is chosen as primary-end point due to the known prognostic value of LVEF. The lower the LVEF, the higher the risk of sudden cardiac death and heart failure. This will compare the overall improvement or change in LVEF between RFA and AAD groups. This end-point will support that either RFA or AADs have an overall better outcome due to significant improvement of LV function with potential impact on morbidity and mortality associated with PVC-CM.

2. *Responders to PVC suppression strategy at 12-month follow-up* (See rationale under Section “Definitions” in 3rd paragraph of Aim 2). Assessment of the number of responders (delta LVEF  $\geq$  10%) after PVC suppression strategies (RFA or AADs) will assess the effectiveness of RFA and AADs to reverse or improve cardiomyopathy induced by frequent PVCs. Evidence that either RFA or AADs is superior to improve or even reverse LV dysfunction in subjects with high burden PVCs could have significant impact of morbidity and mortality including future heart failure and ventricular arrhythmias, and also may avoid ICD implantation.

*The secondary end-points will consist of:*

1. *Efficacy of RFA vs AADs groups to achieve successful PVC suppression at 12-month follow-up, defined as a reduction of PVC burden  $\geq$ 80% (regardless of LVEF change). Understanding the success rate of PVC suppression between RFA and AADs will help better determine the best treatment to those subjects with high PVC burden.*

2. *Composite end-point of adverse events at 12-month follow-up, including worsening in NYHA functional class (I-IV), number of HF and cardiac-related admissions, RFA complications and AAD adverse effects and cardiovascular death.*

This adverse event composite end-point is chosen to understand the overall complications and adverse effects/events related to RFA and AADs. Worsening of NYHA functional class will be defined as when/if the subject’s functional status worsens by one NYHA class. Hospital admissions will be defined as any visit to ED or hospital admissions related only to a cardiovascular event such as heart failure, angina, pre/syncope and palpitations.

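### NYHA class at Observation Visit 1 may come from a visit up to 120 days before enrolment, so the observation-period NYHA change can include change from before the study

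*Combined protocol and SAP*

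**What the plan says.** In Section B, the paragraph on Observation Visit 1 lists NYHA class among the data to collect. It then allows an exception: "Physical examination and NYHA functional class can be completed" "based on a prior visit (up to 120 days prior". The exception covers the physical examination and NYHA class, but not the Minnesota questionnaire.

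For Observation Visit 3 the same section says "appropriate data collection forms should be used to collect current medical therapy, NYHA functional class and Minnesota HF quality of life questionnaire (QOL", with no look-back, and the treatment visits are worded alike. In Table 2 the NYHA entry at Observation Visit 1 carries no look-back footnote, although the echocardiogram and BNP entries do.

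Section C, item c.5, describes NYHA as a questionnaire: "These questionnaires will be provided to each center to be answered by each subject in their local institution", and "All QOL and NYHA questionnaires will be evaluated and graded by an event adjudication committee". Its stated purpose includes assessing "change in quality of life and functional status during the observation period and between both treatment groups". The Project Summary and the Methods paragraph of the Specific Aims also plan to compare functional status, including NYHA class, between the observation period and the suppression strategies.

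Section E makes NYHA worsening a component of the secondary adverse-event composite: "Worsening of NYHA functional class will be defined as when/if the subject’s functional status worsens by one NYHA class". It does not name the visit from which worsening is measured.

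**The concern.** The observation period is the trial's control phase. A change measured over it should start at enrolment and use the same measurement at both ends. The allowance lets the starting NYHA value be up to 120 days older than Day 0, and only at this one visit.

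Two things follow for a subject whose site uses it. First, improvement or deterioration before enrolment is recorded as observation-period change. One plausible direction is toward apparent spontaneous improvement: Section L lists hospital admission with heart failure symptoms among the ways subjects are found, so an older class may reflect a worse state. The documents do not say how often this would happen. Second, the older class was probably recorded by a different method from the class at Observation Visit 3.

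At stake is the pilot's estimate of functional change without PVC suppression, which is meant to inform the full trial. If Observation Visit 1 were also taken as the reference for worsening, the old value would enter the adverse-event composite.

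**Working it through.** **Inputs**
- Look-back for NYHA at Observation Visit 1: up to 120 days (Section B).
- Observation Visit 1: Day 0 (Table 2).
- Observation Visit 3: days 84 to 96 (Table 2).
- Treatment Visit 3, the 3-month visit: "Week 26 (176-188", that is days 176 to 188 (Table 2).

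The plan states no figure for the NYHA interval, so there is none to reproduce.

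**Observation interval as scheduled.** Observation Visit 3 minus Day 0 = 84 to 96 days.

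**Observation interval with the full look-back.** Add 120 days: 84 + 120 = 204, and 96 + 120 = 216. The interval is 204 to 216 days, which is 216/96 = 2.25 to 204/84 = 2.43 times the scheduled one. The share before enrolment is 120/216 = 56% to 120/204 = 59%.

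**Treatment interval for comparison.** From Observation Visit 3 to Treatment Visit 3: shortest 176 − 96 = 80 days, longest 188 − 84 = 104 days.

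**Comparison.** As scheduled, 84 to 96 days of observation are set against 80 to 104 days, which is well matched. With the full look-back, the ratio runs from 204/104 = 1.96 (Observation Visit 3 on day 84, Treatment Visit 3 on day 188) to 216/80 = 2.70 (days 96 and 176). These are limits. A shorter look-back lengthens the interval by less, and a site that does not use the allowance adds nothing.

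**Method of measurement.** No arithmetic applies here.
1. Item c.5 makes the study measure a questionnaire answered by the subject and graded by the adjudication committee.
2. The Recruitment and Informed Consent section requires signed consent before any protocol-specific procedure.
3. A class recorded at a visit before enrolment therefore cannot be that questionnaire.
4. No section says how the earlier class was obtained, or how it would be flagged or handled in analysis. A method difference is thus likely but remains an inference.

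**Which analyses use the Observation Visit 1 value**
- Observation-period NYHA change (Project Summary, Specific Aims, item c.5): yes.
- The own-control comparison in Section F, end of observation against 3 months after suppression: no, because it starts at Observation Visit 3.
- Adverse-event composite (Section E): only if Observation Visit 1 is the reference visit. Table 2 labels both Observation Visit 1 and Treatment Visit 1 as baseline, but schedules no NYHA at the latter.
- LVEF primary endpoints and sample size: no.

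**The case against.** The strongest case against is that the consequences are narrow and partly inferred. The allowance is optional, and using existing clinical data is a deliberate economy in a trial with limited funds. Item c.5 does not limit the questionnaire to later visits, so a class taken on Day 0 would use the same method. Table 2 lists NYHA separately from the Minnesota questionnaire, and only item c.5 calls NYHA a questionnaire. Section F states the own-control comparison from the end of observation, where the old value plays no part. The text also leans toward a pre-treatment reference: Section B calls Treatment Visit 1 the baseline visit, and Section E glosses baseline as pre-treatment for PVC recurrence. All of this stands, and it limits the point to the observation-period NYHA change and an unnamed reference visit.

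Three stronger readings are tempting, and the documents do not support them.
- **That the whole own-control functional comparison is biased.** The Section F comparison is untouched.
- **That the arms are compared unfairly.** A class recorded before enrolment precedes randomization, so any error should be similar in both arms.
- **That a number of false worsenings can be given.** A reader might assume one-class disagreement in 10 to 20% of subjects, half in each direction, and obtain 0.05 × 36 = 1.8 to 0.10 × 39 = 3.9 subjects. That needs an assumed disagreement rate, use of the allowance in every subject and Observation Visit 1 as the reference. The documents give none of these. An even split would also leave no expected net shift, floor and ceiling effects aside.

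The objection does not remove the look-back itself. It is explicit, it applies at one end of a planned comparison, and nothing in the plan corrects for it.

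**Conclusion.** The point holds as a minor design matter. For a subject whose site uses the full allowance, the observation-period NYHA change covers 204 to 216 days instead of 84 to 96, with more than half of that time before enrolment, against 80 to 104 days for the treatment interval. The interval result rests only on the Section B allowance and the Table 2 windows. The likely difference of method rests on the further inference that a pre-consent class was not obtained in an equivalent way.

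The effect on the trial as a whole cannot be sized, because the documents give neither the share of subjects for whom the allowance would be used nor the agreement between the two sources. The composite is exposed only through the unnamed reference visit in Section E.

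**What to change.** 1. In Section B, remove NYHA class from the prior-visit allowance. It may stay for the physical examination. Have every subject complete the study NYHA questionnaire on Day 0, together with the Minnesota questionnaire.
2. In Section E, state that NYHA worsening is measured from Observation Visit 3, the last scheduled NYHA value before treatment. This also keeps pre-treatment change out of the 12-month composite.
3. Flag any prior-visit NYHA values already collected and exclude them from the observation-period NYHA change.

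The cost is one short form at a visit the subject already attends for consent, the Zio Patch and the Minnesota questionnaire. If old values are excluded, a few observation-period NYHA changes will be missing.
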